5.3 Justification

Epilepsy is one of the most common neurological conditions in Africa where it is associated with a great degree of stigma. Most people with epilepsy in this setting do not seek biomedical treatment and only a small proportion of those on treatment take their medication correctly. In fact, the precise magnitude of the epilepsy treatment gap (both the diagnostic and adherence gap) as measured from blood is unknown in urban settings such as Nairobi, where data is urgently needed. Poor adherence and denial of the disorder serve to widen the treatment gap and is associated with impaired quality of life (QoL) and premature mortality. These detrimental consequences can be prevented by improving daily adherence to therapeutic doses of anti-seizure medications (ASMs).

An intervention that utilises a mobile messaging service could remind PWE to take their medication, leveraging on recent increase in mobile phone access over the past 20 years and proven benefit of mobile technology in improving drug adherence for other diseases. The service can also be used to monitor the supply of ASMs to peripheral health facilities. Current on-going studies in the Epilepsy Pathway Innovations in Africa (EPInA) studies in Kilifi and Nairobi are aimed at engaging the county department of health to ensure collaboration in improving care for people with epilepsy. As part of the EPInA studies, we plan to train

primary healthcare workers (PHWs) on diagnosis and management of epilepsy and other mental and neurological disorders using the World Health Organisation's mental health Gap Action Programme-Intervention Guide (mhGAP-IG). These PHWs will be selected from public health facilities in both Kilifi, and Nairobi and these capacity building activities will offer a platform for lobbying for consistent supply of ASMs in the peripheral health facilities. SMS platforms have also been used to set up SMS-based stocktaking forms to monitor supply and reordering of antiretroviral medication to health clinics and this is yet to be explored for ASM supply.

Both text (SMS) and picture messaging (MMS) demonstrate strong potential as tools for healthcare improvement for several reasons: these are accessible on almost every model of mobile phone even basic phones; the cost of transmission is relatively low; neither require great technological expertise, and the transmission of brief health-related messages are widely applicable to a variety of health behaviours and conditions. However, since reading text messages requires some level of literacy, we will compare texts versus graphic messages and the impact on ASM adherence. The messaging service also has the advantage of being asynchronous because it can be accessed at any time that is personally convenient. Use of SMS is more widespread in antiretroviral and antimalarial adherence studies in Africa. This study will further test the evidence to support the use of graphics in impoverished semi-literate communities to convey health-related messages. Improved adherence may subsequently improve quality of life among people with epilepsy, reduce accidental injuries, psychiatric comorbidities, and premature mortality. Nevertheless, it is unclear whether either one of these interventions will improve adherence in a rural population with high rates of illiteracy.

6. TRIAL OBJECTIVES AND PURPOSE

6.1 Null hypothesis

Utilising mobile messaging service to send reminders to people with epilepsy to take anti-seizure medications is not associated with a difference in adherence to anti-seizure medications as measured by detectable and optimal drug levels in blood.

6.2 Primary objective

To examine the effect of sending text or graphic SMS reminders among people with epilepsy in Kilifi and Nairobi, Kenya using a randomized controlled trial design on:

- i. ASM adherence
- ii. Quality of life
- iii. Epilepsy-related stigma scores

6.3 Secondary objective(s)

- (i) Using qualitative methods, to describe the perceptions and perspectives of PWE and their caregivers on the use of text and graphic SMS reminders to improve adherence to ASMs among PWE in Kilifi and Nairobi, Kenya
- (ii) To compare the effectiveness of text versus graphic messaging service or both in improving adherence among people with epilepsy in Kilifi and Nairobi, Kenya
- (iii) To identify the factors associated with an improvement in adherence and improved QoL among PWE and reduction in stigma among PWE and their family members.
- (iv) To document the adverse drug reactions (ADRs) including neurologic and psychiatric ADRs related to frequently prescribed ASMs types and, where possible, plasma levels among PWE in Kilifi and Nairobi, Kenya
- (v) To conduct cost-effectiveness analysis of rolling out the interventions among PWE in Kilifi and Nairobi, Kenya

7.0 TRIAL DESIGN

7.1 Overall Study Design

This study will follow a single-blinded randomized controlled trial design. Participants will be randomly selected from a database of over 3500 PWE. The selected participants will be invited to the clinic for screening against the eligibility criteria and enrolment into the study. The study sample will consist of 1,200 people with epilepsy in each site. Out of the 1200 PWE, there will be 900 participants in the intervention arm (300 receiving text SMS, 300 receiving graphic SMS, 300 receiving both text and graphic) and 300 in the control arm (non-epilepsy related SMS) (Figure 1). The participants will be aware of the intervention status, but the researcher and clinical staff will not. All participants will receive an SMS (cases to

encourage adherence and controls will receive non-epilepsy related messages) for comparability and to reduce the risk of disclosing the blind during follow up visits. Participants will be encouraged to not disclose the content of their messages during follow up visits. As a secondary outcome, ASM-related ADRs including neurological and psychiatric ADRs, will be documented for all participants on ASMs, and where possible, related to type (s) of ASM used.

7.2 Description of the study areas and population

This study is part of the EPIInA studies planned in Kilifi and Nairobi. In Kilifi, the SMS trial will take place within the Kilifi Health and Demographic Surveillance System (KHDSS). The KHDSS was established in 2000, covers a defined geographical area of 900km² located on the Kenyan coast and currently has a population of about 280,000 residents under active surveillance <https://kemri-wellcome.org/programme/health-research-linked-to-a-demographic-surveillance-system/>. We will approach people with epilepsy currently taking ASMs from a database of over 3,500 patients attending the epilepsy clinic routinely. Written consent and/or assent (for children aged 13 to 17 years old) will be obtained from all participants and the study will be conducted with permission from a local ethics review committee.

In Nairobi County, we are collaborating with APHRC, through their Nairobi Urban Health and Demographic Surveillance System (NUHDSS). The NUHDSS is in Nairobi city comprising two slum communities namely Korogocho and Viwandani, both with a total population of about 65,000 (Beguy et al., 2015). All houses are marked with unique identification numbers making it possible to obtain vital information on not only sociodemographic patterns but also pregnancy outcomes and movement in and out of NUHDSS. Children and adolescents comprise 35% of the total population. In 2012, the crude birth-rate was 28.9/1000 person-years, while mortality rate was 6.2/1,000 person-years. The NUHDSS offers an opportunity to conduct studies investigating the link between urbanisation, poverty, or lack of social amenities on health outcomes (Kimani-Murage et al., 2015). Additionally, participants attending one KAPE-led clinic in Nairobi will also be invited to participate in the study.

8.0 DESCRIPTION OF THE INTERVENTION

8.1 Intervention

The intervention will be a short message service (SMS) reminder sent to the mobile phones of participants in the intervention group reminding them to take their anti-seizure medications. This will be a behavioural intervention with no investigational medicinal product. Each SMS (text or graphic or both) adherence message will be 120–140 characters long. To increase the probability that that the PWE or family member will read the messages and support family members with epilepsy, message will be randomly complemented with a quote (up to 60 characters long) and unrelated to epilepsy treatment, but designed to be motivating, entertaining, or merely attention-getting. This motivational element was used with success in the health workers adherence to antimalarial guideline studies. The graphics will be hand drawn by a local illustrator and the accompanying text of no more than 15 characters will be scanned and sent as low-resolution jpeg files, suitable for the MMS format that is compatible with basic phones.

8.2 Identity of the SMS

We will use a validated software for the automated bulk SMS service and outsourced tool for the MMS transmission. The SMS company contracted will assist in the setting up and training of the software, plus on-going support. The SMS interface/platform will utilize an android application system for smartphones and Unstructured Supplementary Service Data (USSD) format for basic phones and will be accessible from a web browser and will be integrated into an encrypted central database. All requests and administrative actions made to the program and its responses will be logged chronologically and stored in the database.

8.3 Frequency and timing of sending messages

The messages will be transmitted at a frequency and time, determined during focus group discussions held before the roll-out of the intervention, that is convenient for both the PWE and their caregivers.

8.4 SMS dispensing procedures

Automated reminder messages will be sent out by the KEMRI-Wellcome Trust Research Programme data manager and from a password-protected computer within the Neuroscience Unit in Kilifi. These will be sent as mobile phone texts (SMS) or graphic picture messages (MMS).

8.5 Intervention Compliance

It will be possible to view a delivery report of whether the messages were received or not due to network issues. After the screening visit, all participants will be contacted via phone call to check that their phones can receive the messages. Prior to the commencement of the SMS trial, ongoing EPInA studies will conduct engagements with the respective county departments of health on sustained availability of ASM at the health facilities within the study area where PWE are likely to visit for medication refill. Primarily PWE will visit the study clinics (epilepsy clinic in Kilifi, two APHRC clinics in Nairobi and one KAWE-led clinic in Nairobi). However, due to ongoing capacity building and task sharing studies in Kilifi (the mhGAP study), some PWE may visit any of the 128 public peripheral health facilities already contributing primary health care providers for training. Since adherence may also be affected by availability of medications, we hope to be able to lobby for the set-up of an SMS platform to monitor supply and re-ordering of ASMs in Kilifi and Nairobi County in addition to ongoing engagements with the counties as part of capacity building and task sharing within the EPInA studies.

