An intervention that utilises a mobile messaging service could serve to remind patients with epilepsy (PWE) to take their medication. This has not been undertaken before and is now feasible because of greater mobile network coverage in rural areas in Kenya and increasing mobile phone ownership and usage in these areas. Use of SMS is more widespread in antiretroviral and antimalarial adherence studies in Africa and has shown great promise in improving adherence to medication and consequently, outcomes. This study will further test the evidence to support the use of graphics in impoverished semi-literate communities such as the study sites to convey health-related messages. These multi-media messages will be designed in a simple format that is compatible with both basic phones and smart phones. However, since the display characteristics of basic phones and smart phones may differ, we will document the type of phone used by the participant and this will be taken into consideration during the analyses and interpretation of findings. It is unclear whether either one of these interventions will improve adherence in a rural population or informal settlements with high rates of illiteracy.

A two-way SMS platform will be implemented such that PWE participating in the study will be able to receive messages from the study team and send messages to the study team via normal text or using an unstructured supplementary service data (USSD) prompt at no cost to the PWE. The SMS platform will also be able to send delivery reports to the study team if the message is delivered to the intended user and a read report once the message is opened by the intended user. During planned follow up visits, we will also check for any issues regarding receiving messages, disruptions in the network service provider or electricity, change of phone number, change of handsets and whether caregivers relay messages to the PWE in the case that they are the ones receiving the SMS on behalf of the PWE. Those who do not relay messages will be encouraged to do so and changes in phone numbers will be updated. Since this is meant to be a pragmatic trial that can be rolled out in a sustainable fashion throughout resource-poor settings, challenges are to be expected and will be taken into consideration when interpreting the findings.

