9.2.2 Eligibility criteria

9.2.2.1 Inclusion criteria

- (i) Children or adults with a diagnosis of epilepsy ascertained by a clinician at the epilepsy clinic
- (ii) Taking anti-seizure medications at the time of the study
- (iii) Living within an area defined as the Kilifi Health Demographic Surveillance System, or the Nairobi Urban Health and Demographic Surveillance System at the time of the study or attending the epilepsy clinic in Kilifi or a KAWE-led clinic in Nairobi
- (iv) Able to give written informed consent or assent in addition to parental consent (if aged between 13 and 17 years old) to participate in the study either by themselves or in the presence of an independent witness

(v) Access to a basic mobile phone in the household

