9.2.3 Consenting/Assenting and screening for eligibility

Consenting and/or assenting (for children aged 13 to 17 years old) will be done by field workers during initial contact and participants booked for the first study visit. Investigators will emphasize that participation in the study is voluntary. All participants will have the study explained to them including potential risks and obligations before giving written informed consent and/or assent. Once consented and/or assented, participants will be screened for eligibility based on the above-mentioned set of inclusion and exclusion criteria. Screening will be conducted by study fieldworkers in collaboration with the study clinicians.

Participants who meet the inclusion criteria at the screening visit will be telephoned by a fieldworker a week prior to sending out the SMS to assess availability of mobile phone access. They will also be asked about any new medical complaints and concomitant medication since their screening visit.

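### No test picture is described before randomisation, so a text v graphic difference could not be traced to format rather than to handsets that never showed the picture

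*Combined protocol and SAP*

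**What the plan says.** **Before messages start.** Section 8.5 has all participants "contacted via phone call to check that their phones can receive the messages" after the screening visit. Section 9.2.3 describes a call in which eligible people are "telephoned by a fieldworker a week prior to sending out the SMS to assess availability of mobile phone access". Table 1 lists one call, at week -1, to check phone availability and accessibility, ahead of randomisation at month 0. None of these places says how reception is checked, and none mentions a test picture.

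**Eligibility.** Section 9.2.2.1 requires only "Access to a basic mobile phone in the household".

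**Picture format.** Under section 8.1 the graphics carry at most 15 characters of text and are "sent as low-resolution jpeg files, suitable for the MMS format that is compatible with basic phones". Section 8.2 specifies the platform as "Unstructured Supplementary Service Data (USSD) format for basic phones" and does not explain how that fits with picture delivery.

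**Handset differences.** Section 5.2 accepts the problem, "since the display characteristics of basic phones and smart phones may differ", and responds that "we will document the type of phone used by the participant and this will be taken into consideration during the analyses".

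**Other safeguards.** Sections 5.2, 8.5 and 9.2.6(iii) plan delivery reports, read reports and a prompt with each message asking whether it was read. Section 5.2 adds questions at follow-up visits about reception problems and changed handsets. Section 12.2.1 has the contractor test the SMS/MMS gateway.

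**Analysis.** Sections 12.2.1 and 12.2.2 give phone type, read status and confirmed receipt no place in any model or analysis set.

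**The concern.** Comparing text with graphic messages, or both, is secondary objective (ii) in section 6.3, and section 5.3 motivates graphics by low literacy. A participant in the graphic-only arm whose phone cannot show the picture receives almost no reminder, because the accompanying text is so short. A text-arm participant with the same phone receives the full message. The graphic arm would then look worse for a technical reason, and the result could be read as evidence against pictures for people who cannot read.

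The planned safeguards do not settle this:

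- Phone type is a proxy for display, not a test of it.
- Read reports and replies show that a message was opened or acknowledged, not that the image appeared.
- In the text-only arm, reports and replies concern text messages. They cannot identify the text-arm phones that would have shown a picture, which a like-for-like comparison needs.
- Section 13.3 lets the team withdraw people who are not accessing SMS, so picture failure could also cause unequal withdrawal between arms.

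**Working it through.** **The plan's own figures.** Section 12 states no alpha; two-sided 5% is assumed. All calculations use the two-proportion normal formula with pooled variance and no continuity correction.

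- Table 2, 50% column entry at 95% power: 30% v 50% needs 153 per arm; 153 × 1.5 × 1.1 = 252.45, against 253 stated. The same 30% control rate reproduces the other eight cells to within about one participant.
- The 95% power in the text of section 12.1: effective n = 300 × 0.9 / 1.5 = 180. If the 50% improvement is relative to 38% adherence (100% minus the 62% gap), 38% v 57% gives power 0.954.

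**Inputs for the check**

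- Adherence 30% in control and 50% with a reminder that is seen (the rates behind Table 2).
- 300 per arm per site, 20% loss to follow-up and design effect 1.5 (section 12.1): effective n = 300 × 0.8 / 1.5 = 160 per arm per site, 320 with both sites pooled.
- Share f of the graphic-only arm whose phone never shows the picture. This is **not in the documents**; 10%, 30% and 50% are assumed.
- Text and graphic are equally effective once seen, and people who never see the picture behave like controls.

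**Formulas**

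- Graphic-arm adherence: pG = 0.30 + 0.20 × (1 − f).
- Chance of a significant result in a given direction: Φ[(d − 1.96·s0)/s1], where d is the difference in proportions, s0 = √(2·p̄(1 − p̄)/n), s1 = √([p1(1 − p1) + p2(1 − p2)]/n) and p̄ is the mean of the two proportions.

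**Worked case, f = 30%, one site**

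- pG = 0.30 + 0.20 × 0.70 = 0.44.
- Text v graphic: d = 0.06, s0 = 0.0558, s1 = 0.0557; (0.06 − 1.96 × 0.0558)/0.0557 = −0.886, so the probability is 0.188.
- Graphic v control: d = 0.14, s0 = 0.0540, s1 = 0.0534; (0.14 − 1.96 × 0.0540)/0.0534 = 0.640, so power is 0.739.

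**Results**

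| Assumed failure f | Graphic-arm adherence | Significant for text, one site | Significant for text, both sites | Power, graphic v control, one site |
|---|---|---|---|---|
| 0% | 50% | 2.5% | 2.5% | 96% |
| 10% | 48% | 5.5% | 7% | 91% |
| 30% | 44% | 19% | 33% | 74% |
| 50% | 40% | 43.5% | 72% | 47% |

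**Sensitivity.** With 38% v 57% and effective n 180 (360 pooled), the chance of a result favouring text at 10%, 30% and 50% failure is 5.5%, 19% and 44% per site and 7%, 34% and 72% pooled. Power for graphic v control falls from 95% to 91%, 72% and 45%. The pattern does not depend on which of the plan's two adherence baselines is used.

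**The case against.** **Failure would not go unmonitored.** A reader might infer that the call is the trial's only check. It is not: the reports, prompts, visit questions and phone-type record are all planned. What stands is that the checks that follow individual messages start after allocation, the gateway test concerns the sending side, and none confirms display.

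**The call may include a test.** Section 8.4 counts both SMS and MMS as messages, so the purpose stated in section 8.5 covers pictures. The documents neither describe nor exclude a test message, so they do not support saying that the call cannot detect a failure. The supportable point is that the method is not described, while section 9.2.3 and Table 1 frame the call as one about phone access.

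**Half the trial is not at stake.** Two of the four arms receive pictures, but the combined arm also receives text, so a failed picture there still leaves a reminder. Only the graphic-only arm can go untreated for this reason.

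**The comparison is not invalid.** Section 5.2 calls the trial pragmatic and expects such difficulties. If pictures fail on the phones people own, that is part of the effect of offering pictures. This stands in full: the all-randomised contrast is valid for that question, and only its cause is unclear.

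**The size is uncertain.** The protocol says the files are "suitable for the MMS format that is compatible with basic phones", and nothing in it supports a failure rate of 30% or 50%. Leaving out the design effect would give larger figures for text v graphic (6%, 26% and 60% per site; 9%, 46% and 88% pooled), but section 12.1 sizes the trial with 1.5, so it belongs in both contrasts.

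**Conclusion.** The point holds in a limited form. No described step before randomisation establishes, in any arm, which phones can show a picture, and no prespecified analysis uses phone type or receipt. A text v graphic difference would therefore be interpretable as the effect of offering each format, but not as evidence about the format itself.

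How much this matters depends on a failure rate that the documents do not give. It is small at 10% and material from 30% upward, both for text v graphic and for graphic v control. These sizes also assume equal effectiveness once a message is seen and control-level adherence where the picture fails. The documents do not support saying that handset failure will decide the comparison. They support saying that the trial could not tell whether it had. Because the rate is unknown and cheap to measure, this is a worthwhile low-cost improvement, not a flaw that undermines the trial.

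**What to change.** - At the week -1 call, before randomisation, send one test text and one test picture to every candidate's registered phone. Have the recipient confirm receipt and display of each, for example by describing the picture. Correct wrong numbers at the same time.
- Record text seen and picture seen as baseline variables in all four arms. Every candidate gets the same two messages before allocation, so the test reveals nothing about the assigned arm.
- Leave eligibility unchanged and keep the all-randomised comparison as the main text v graphic analysis.
- In section 12.2.2, prespecify a supportive text v graphic comparison restricted to phones confirmed as picture-capable at baseline, and say how phone type will be used.

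The cost is two messages and a few minutes per candidate in a call already planned. The supportive comparison will be smaller: at 30% failure, 160 × 0.7 = 112 effective participants per arm per site. It should be presented as an aid to interpretation, not as a second confirmatory test.
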